4.4 Start of Trial and End of Trial

The study will be a single-center trial intended to start in the fourth quarter of 2024 with the recruitment of the participants according to the inclusion/exclusion criteria and initial signing of the

Clinical Study: ES2B-C001-S01 EU CT No.: 2024-516333-12-00

Informed Consent Form (ICF). The end of this trial is expected in the first quarter of 2026. The end of the trial is defined as the date of the last visit of the last patient in the trial or last scheduled procedure shown in the schedule of activities for the last patient in the trial.

A patient is considered to have completed the trial if the patient has completed all periods of the trial including the last scheduled procedure shown in the SoA in Section 1.3.

[figure not shown]
opulation
opulation

5.3 Inclusion Criteria
Patients are eligible to be included in the trial only if all of the following criteria apply:
The state of the s
5.4 Exclusion criteria
Patients are excluded from the trial if any of the following criteria apply:

Clinical Study: ES2B-C001-S01 EU CT No.: 2024-516333-12-00

5.5 Contraceptive rules

5.5.1 Women Participants

Females of childbearing potential must use highly effective methods of contraception Table 5, of which one at least is a barrier method, from screening until the end-of-study visit (or minimum 4 weeks after receipt of the IMP).

Table 5: Highly effective methods of contraception.

	Highly effective methods of contraception
1.	Total abstinence (when this is in line with the preferred and usual lifestyle of the participant). Periodic abstinence (e.g., calendar, ovulation, symptom-thermal, post-ovulation methods) and withdrawal are not acceptable methods of contraception.
2.	Female sterilization (have had surgical bilateral oophorectomy with or without hysterectomy), total hysterectomy, or tubal ligation at least 6 weeks before taking study intervention. In case of oophorectomy alone, only when the reproductive status of the woman has been confirmed by follow-up hormone level assessment.

Clinical Study: ES2B-C001-S01 EU CT No.: 2024-516333-12-00

3.	Sterilization of male partner (at least 6 months prior to screening) with post-procedural semen specimen to verify a successful procedure (the report of the male partner will not be collected since the partner is not study participant). For female participants on the study, the vasectomized male partner should be the sole partner for that participant.
4.	Placement of an intrauterine device or intrauterine system, or other forms of non-hormonal contraception that have comparable efficacy (failure rate < 1%).

Female participants as described in Table 6 are considered NOT to have childbearing potential and do not need to receive contraceptive advice. Treating physicians are advised to refer their participant for a gynecological opinion if at all unsure as to whether a woman meets the criteria for being of non-childbearing potential.

Table 6: Women not considered to have childbearing potential.

	Women not considered to have childbearing potential
1.	Age equal to or more than 50 years (≥ 50 years) and naturally (spontaneously) amenorrhoeic (postmenopausal) for ≥12 months*.
2.	Premature ovarian failure confirmed by a specialist gynecologist.
3.	Previous surgically sterilized (have documented sterilization) as one of the following: bilateral oophorectomy or bilateral salpingectomy at least 90 days before the start of the trial and/or hysterectomy. NOTE: Documentation as per review of the participant's medical records, medical examination, or medical history.
4.	Turner syndrome, uterine agenesis.

^{*} A postmenopausal state is defined as no menses for 12 months without an alternative medical cause.

5.5.2 Male Participants

Male participants with female partners of childbearing potential are eligible to participate if they agree to ONE of the criteria defined in Table 7 for the duration of the study until 90 days after the last dose of study intervention.

Table 7: Contraception rules for male participants – at least ONE needs to apply

	Contraception rules for male participants
--	---

Clinical Study: ES2B-C001-S01 EU CT No.: 2024-516333-12-00

1.	Agree to use a male condom (not made of natural [animal] membrane [e.g., latex, or polyurethane condoms]) plus partner use of an acceptable contraceptive method. Plus, female partners of childbearing potential must agree to use one of the acceptable contraceptive methods.
2.	Males with a pregnant or breastfeeding partner must agree to remain abstinent from penile-vaginal intercourse or use a male condom during each episode of penile penetration.
3.	Must agree to abstain from donating semen or sperm for the duration of the study and for 90 days after the dose(s) of study intervention.

Female partners of childbearing potential (even if they have amenorrhea) must agree to use one of the contraception methods described in Table 8 during the following time periods related to this study: 1) for at least 28 days before the dose(s) of study intervention in the male participant; 2) during the study; and 3) until 90 days after the dose(s) of study intervention. The adequacy of other methods of contraception will be assessed on a case-by-case basis by the PI.

Table 8: Contraception methods for female partners of childbearing potential – at least ONE needs to apply

	Contraception methods for female partners of male participants
1.	Intrauterine device.
2.	Diaphragm combined with spermicidal foam/gel/film/cream/suppository.
3.	To practice complete (absolute and continuous) abstinence from heterosexual contact.

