8.4.6 Pregnancy and Postpartum Information

Any female participant who becomes pregnant while participating in the study will discontinue study intervention or will be withdrawn from the study. The PI must follow-up and document the course and the outcome of all pregnancies, including those of female partners of male participants, even if the subject was withdrawn from the clinical study or if the clinical study has finished.

The Investigator will collect pregnancy information on any female participant, or female partner of a male participant, who becomes pregnant while participating in this study. Information will be recorded on the appropriate form and submitted to the Sponsor within 24 hours of learning of a participant's or female partners pregnancy and the pregnant woman will be referred to a physician specialized or experienced in teratology for evaluation and advice. The participant will be followed to determine the outcome of any pregnancy. All outcomes of pregnancy must be reported by the PI to the Sponsor on the pregnancy outcome report form within 24 hours after he/she has gained knowledge of the delivery or elective abortion.

The Investigator will collect any follow-up information on the participant/female partner and the neonate, and the information will be forwarded to the Sponsor. Generally, follow-up will not be required for longer than 6 to 8 weeks beyond the estimated delivery date. Any termination of the pregnancy will be reported, regardless of fetal state (presence or absence of anomalies) or indication for the procedure.

Pregnancy alone is not regarded as an AE unless there is a suspicion that the study drug may have interfered with the effectiveness of a contraceptive medication. Elective abortions without complications should not be regarded as AEs, unless they were therapeutic abortions (see below). While pregnancy itself is not considered to be an AE or SAE, any pregnancy complication or elective termination of a pregnancy will be reported as an AE or SAE. A spontaneous abortion is always considered to be an SAE and will be reported as such. Any post-study pregnancy-related SAE considered reasonably related to study intervention by the Investigator will be reported to the Sponsor. While the Investigator is not obligated to actively seek this information in former study participants, he or she may learn of any pregnancy related information through spontaneous reporting.

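### Section 5.5.2 and the Table 7 heading ask a man to accept only ONE of three rows that are separate duties, so his own condom or abstinence commitment, or his commitment not to donate sperm, can drop out

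*Protocol*

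**What the plan says.** The lead-in of Protocol section 5.5.2 is restricted to some men: "Male participants with female partners of childbearing potential are eligible to participate". The condition it sets is that they are "eligible to participate if they agree to ONE of the criteria defined in Table 7", for the study and until 90 days after the last dose. The heading of Table 7 carries the same rule: "Contraception rules for male participants – at least ONE needs to apply".

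The three rows of Table 7 are:

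- Row 1: a male condom, together with an acceptable contraceptive method used by the partner.
- Row 2: "Males with a pregnant or breastfeeding partner must agree to remain abstinent from penile-vaginal intercourse or use a male condom".
- Row 3: "Must agree to abstain from donating semen or sperm for the duration of the study and for 90 days", counted after dosing.

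The paragraph after Table 7 adds a rule that does not depend on which row the man picks. Female partners of childbearing potential "must agree to use one of the contraception methods described in Table 8", from at least 28 days before dosing until 90 days after it. Table 8 offers an intrauterine device, a diaphragm with spermicide, or complete abstinence, and the investigator judges other methods case by case.

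For women, section 5.5.1 requires Table 5 methods, at least one of them a barrier method.

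**The concern.** A choose-one rule is sound when the items are substitutes. Table 8 is such a list: each row is a different way to the same end. Table 7 is not. Its rows address different exposures: conception with a fertile partner, exposure of a pregnant or breastfeeding partner, and donated semen. Row 2 is conditional on the man's situation, so it cannot be an option open to every man. Row 3 is not a contraceptive measure and carries its own duration, as a standing duty would. Rows 2 and 3 also say that the man must agree, which conflicts with a rule that lets him pass them over.

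At stake is a participant- and partner-protection rule in a first-in-human trial of a product whose clinical safety profile the protocol calls unknown (section 2.3). A site that applied 5.5.2 to the letter could accept a man's agreement as complete when one or more of these duties had never been put to him.

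**Working it through.** The plan states no figure on this point, so there is none to reproduce. The check is to apply the choose-one rule to each row and see which duties remain.

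| Row agreed to alone | Man's condom or abstinence, partner of childbearing potential | Man's condom or abstinence, pregnant or breastfeeding partner | No sperm donation | Table 8 method by partner of childbearing potential |
|---|---|---|---|---|
| Row 1 | Condom: yes | Row 2 not agreed; row 1's condom duty only | No | Kept |
| Row 2 | Only as far as row 2 reaches | Yes | No | Kept |
| Row 3 | No | No | Yes | Kept |

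1. **No single row covers all the duties.** Sperm donation is left open in 2 of the 3 cases, and the man's own condom or abstinence commitment is wholly absent in 1 of the 3.
2. **The mandatory wording conflicts with the rule.** Rows 2 and 3, 2 of the 3, word the man's own part as something he must agree to.
3. **The lead-in is narrow.** It names only men with partners of childbearing potential, so within 5.5.2 no other man is bound to row 3.
4. **The last column does not change.** The Table 8 requirement sits outside Table 7 and holds whichever row is chosen. If the couple meets it by complete abstinence (Table 8 row 3), the missing condom has no consequence for them. If they meet it by a device or diaphragm, partner contraception is in place but the man's condom is not.
5. **A breastfeeding partner is not clearly outside Table 8.** Section 5.5.1 says "Female participants as described in Table 6 are considered NOT to have childbearing potential", and breastfeeding is not in that table. Table 6 is written for participants, so it only suggests how a partner would be classed. If she counts as of childbearing potential, she keeps a Table 8 method and only row 2's condom-or-abstinence element is lost.
6. **Section 8.4.6 does not fill the gap.** The investigator will "collect pregnancy information on any female participant, or female partner of a male participant, who becomes pregnant while participating in this study". That acts after a pregnancy has occurred.

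Duration, for context only: the end-of-study visit is at week 18 (section 8.3.5.1) and falls 6 weeks after the last dose (section 6.8), so the last dose is at week 12, which agrees with the fifth dose in section 8.3.5.2. The man's duties therefore run nominally 12 × 7 + 90 = 174 days from the first dose. This is how long the duties last. It does not measure the defect.

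Section 5.5.1, checked the same way: Table 5 lists abstinence, female sterilization, partner sterilization, and an intrauterine device or system or an unnamed non-hormonal method with a failure rate below 1%. Barrier methods named: 0 of 4 rows.

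**The case against.** The strongest reply is that the main protection is intact. Partner contraception is required separately, for every partner of childbearing potential, with case-by-case judgement by the investigator. This stands. A reader might infer from the choose-one rule that a couple could be left with no contraception at all; the paragraph after Table 7 rules that out for partners of childbearing potential.

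A second reply is that enrolment depends on the inclusion and exclusion criteria (section 6.5), and the lists in 5.3 and 5.4 are not visible. They may contain contraception wording that closes the gap. This also stands. A reader might infer that men without these commitments will be enrolled; the document does not show that.

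A third reply is that the heading sets a minimum, that row 2 limits itself to the men it concerns, and that sensible staff would treat the mandatory wording as duties. Some would. But the lead-in says ONE without qualification and the heading supports it, so staff would have to depart from the stated condition to reach the intended result. This is an internal inconsistency, and there is no sign that anyone chose it as a design.

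For women, a reader might infer from Table 5 that protection is missing. It is not. The barrier clause errs on the strict side, reads naturally as a second method added to the first, and is backed by pregnancy tests at screening, dosing days and follow-up (section 8.3.7). It is a wording point only.

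**Conclusion.** The rule in 5.5.2 and the Table 7 heading is wrong as written. It treats separate duties as alternatives, so a man can satisfy Table 7 without committing to a condom or abstinence, including with a pregnant or breastfeeding partner, or without committing to refrain from sperm donation. It also leaves men without a partner of childbearing potential outside the donation rule.

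The conclusion rests on a literal reading of section 5.5 alone. Partner contraception under Table 8 is unaffected. The consequence cannot be counted in patients: neither the number of men nor the number of women of childbearing potential among the 9 to 27 patients is given, and either may be small. No endpoint, dose decision, sample size or analysis changes. It should be corrected because it is an operative protection rule and the correction is easy.

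**What to change.** In the 5.5.2 lead-in and the Table 7 heading, replace ONE with 'all criteria that apply', and widen the lead-in to all male participants. Then state whom each row binds:

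- **Row 1:** men with a non-pregnant partner of childbearing potential, unless the couple practises complete abstinence as in Table 8 row 3. Without these two exceptions the edit would impose partner contraception during pregnancy and a condom on abstinent couples.
- **Row 2:** men with a pregnant or breastfeeding partner. A breastfeeding partner of childbearing potential still uses a Table 8 method.
- **Row 3:** all male participants.

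Table 8 keeps its at-least-one rule.

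Minor: in 5.5.1, either state the barrier method as an addition to a Table 5 method or delete the barrier clause. Which is right is for the sponsor.

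The cost is wording, plus matching consent text where it repeats these rules. No visits, patients or data are added. A man unwilling to accept every row that applies to him would not qualify, and men without a partner of childbearing potential would now be bound by the donation rule.

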5.6 Screen Failures

A screen failure occurs when a patient who has consented to participate in the clinical trial is not subsequently assigned to trial treatment.

A minimal set of screen failure information is required to ensure transparent reporting of screen failure patients to meet the CONSORT publishing requirements and to respond to queries from regulatory authorities. As a minimum, the following data will be collected in the eCRF for screening failures: demography, screen failure details and eligibility criteria.

Re-screening of screening failures is not allowed. However, if the reason for screening failure is not due to the patient failing to meet the eligibility criteria but is administrative or operational (e.g. reserve patient or screened patients who were not dosed within the screening window due to time constraints), re-screening may be permitted.

Clinical Study: ES2B-C001-S01 EU CT No.: 2024-516333-12-00

6 Trial Intervention and Concomitant Therapy

ES2B-C001 is a therapeutic cancer vaccine comprised of a capsid virus-like particle (VLP) decorated with the human HER2 receptor.
ES2B-C001 is formulated as a solution for intramuscular (I.M.) injection and will be administered with or without the adjuvant mixed at a v:v ratio of 1:1.
Table 9 describes the intervention to be administered during the trial period, including route/mode of administration, dose, dosage regimen, duration of intervention.

All trial products are supplied to sites by the sponsor.

6.1 Description of Trial Intervention

Table 9: Trial Intervention(s) Administered

Clinical Study: ES2B-C001-S01 EU CT No.: 2024-516333-12-00

6.2 Rationale for Dose

In the GLP repeat-dose toxicity study in cynomolgus monkeys, 8 intramuscular injections of ES2B-C001 alone were locally and systemically well tolerated with no evidence of systemic toxicity at 750 µg/dose. However, ES2B-C001 emulsified in [adjuvant] showed a poor local tolerance at injection sites at dose levels Based on these results, the no observed adverse effect level (NOAEL) was considered to be for ES2B-C001 alone and for ES2B-C001 together with [adjuvant]
Although the WHO guideline does not specifically apply to therapeutic vaccines for non-infectious diseases, our starting dose considerations are aligned with its principles. Hence, the doses planned to be used in humans are in the range of therapeutically active doses in animals on a dose per subject basis.
The dose ranges chosen for this trial are anticipated to be immunogenic, with the expectation for an immune response being fairly conservative even at the lowest dose. This assumption is based on immunogenicity results across three species: mouse, rat and cynomolgus monkey. For instance, the sera of Delta 16 mice vaccinated twice 2 weeks apart with 5-40 µg adjuvanted ES2B-C001 strongly inhibited tumor growth in vitro . An increase in the anti-HER2 antibody titers was seen when increasing the dose from 5 to 10 µg, but titers plateaued at higher doses, with no substantial increase seen from 20 to 40 µg. Furthermore, administration of adjuvanted ES2B-C001 to Delta16 FVB mice completely blocked tumor development, whereas all control mice had lung nodules. Non-adjuvanted ES2B-C001 prevented tumor development in 6/9 mice (67%), while the remaining mice had 1-2 lung nodules only. On a body weight basis, the starting dose has a safety margin of 2000 (mice of 20 g body weight versus women of 40 kg body weight). Taken together, the planned starting doses in this study in BC patients are considered to be safe, but still sufficient to induce an immune response and thereby inhibit tumor growth.
The pre-planned dose levels and dose increments are shown in Table 10.

[figure not shown]
The dose escalation steps may be smaller, but never larger, dependent on the safety evaluation by the DSMB and the Sponsor's safety committee.

In case the first dose level is found to be dose limiting, a lower dose level may be investigated at a level recommended by the DSMB and agreed upon in Sponsor's safety committee.

Clinical Study: ES2B-C001-S01 EU CT No.: 2024-516333-12-00

Table 10: Pre-planned dose levels of ES2B-C001

^{*}If the DSMB suggests investigating additional dose levels, any additional cohort for adjuvanted or non-adjuvanted treatment will be named A- or NA-cohort-X.

6.3 ES2B-C001 Dosing and Administration

In this trial ES2B-C001 should only be administered in a hospital or clinic with immediate access to equipment, medications, and appropriately qualified staff for resuscitating and stabilizing individuals in an acute emergency, along with ready availability of an intensive care unit and other hospital facilities.

Each administration of adjuvanted or non-adjuvanted ES2B-C001 will be given in the shoulder, thigh, or buttocks (alternating) by an authorized site staff proficient in English. If axillary lymph nodes have been resected on one side, the shoulder on that side should not be used for vaccination, if only 1 or 2 sentinel nodes have been removed administration may be done in the corresponding shoulder. If a region planned for administration of adjuvanted or non-adjuvanted ES2B-C001 has any clinically significant findings on day of dosing (e.g., swelling or ulceration) an alternative administration site must be chosen. Selection of region for injection should be done considering SoC treatments and allow for preferred regions for SoC to be used for that purpose (and not the vaccine).

All administrations of adjuvanted or non-adjuvanted ES2B-C001 in the ambulatory setting must be undertaken allowing for in-person monitoring and observation period of one hour following the injections.

The IMP Manual contains specific instructions for the preparation of the solutions and administration, including how to prepare the adjuvanted formulation of the final product, mixing [adjuvant] with ES2B-C001 solution.

6.4 Preparation, Handling, Storage, and Accountability

The investigator or designee must confirm appropriate conditions (e.g., temperature) have been maintained during transit for all IMP received, and any discrepancies are reported and resolved before use of the trial intervention. Only patients enrolled in the trial may receive adjuvanted or

Clinical Study: ES2B-C001-S01 EU CT No.: 2024-516333-12-00

non-adjuvanted ES2B-C001, and only authorized site staff may supply, prepare, or administer adjuvanted or non-adjuvanted ES2B-C001.

All trial supplies must be stored in a secure, environmentally controlled, and monitored (manual or automated) area in accordance with the labeled storage conditions with access limited to the investigator and authorized site staff.

The investigator, or authorized site staff is responsible for accountability, reconciliation, and record maintenance (i.e., receipt, reconciliation, and final disposition records) throughout the clinical study. The drug accountability log includes information such as, subject number, randomization number, amount dispensed and remaining amount. The remaining IMP volume per vial will be stored until monitor reconciliation.

The used/opened vials should be marked as 'used' and kept separate from the products not yet dispensed. All dispensing and accountability records will be available for Sponsor review. When the Study Monitor visits the study site, he/she will reconcile the drug accountability log with the products stored at the study site IMP storage.

Packaging and labelling of ES2B-C001 will be outsourced to a clinical packaging contract manufacturing organization. All products are labelled according to Annex 13, EudraLex, volume 4 and local requirements. Each unit of product is uniquely numbered.

After receiving Sponsor approval in writing, study site is responsible for returning all unused or partially used study medications to the Sponsor or designated third party or for preparing the study medications for destruction via incineration. Further guidance and information for the final disposition of unused IMP are provided in the IMP Manual.

The trial interventions supply, packaging, labeling, and storage are outlined in Table 11.

Table 11: Trial intervention packaging, storage, and handling.

Trial intervention	Supplier	Packaging	Labeling	Storage	Storage after preparation
ES2B-C001	ExpreS2ion Biotechnologies ApS	10 vials per box. The primary packaging will be glass 2R vials which will be closed with rubber stoppers.	according to applicable local and regulatory	-25°C to -15°C	15°C to 25°C

Clinical Study: ES2B-C001-S01 EU CT No.: 2024-516333-12-00

Trial intervention	Supplier	Packaging	Labeling	Storage	Storage after preparation
[adjuvant]	ExpreS2ion Biotechnologies ApS	10 vials per box. The primary packaging will be amber glass 2R vials which will be closed with rubber stoppers.	according to applicable local and regulatory requirements	15°C to 25°C	15°C to 25°C

